10.7. Appendix 7: Kidney Safety: Monitoring Guidelines

10.7.1. Laboratory Assessment of Change in Kidney Function and Detection of Kidney Injury

Standard kidney safety monitoring requires assessment of baseline and postbaseline serum creatinine. Additionally, baseline and postbaseline serum Scys makes it feasible to distinguish AKI from other causes of Scr increase. In this study, eGFR will be determined using the 2021 CKD-EPI Scr-Scys combined equation (see Table below) and both Scr and Scys will be measured as part of the protocol-required safety laboratory assessments at all times specified in the SoA.

Regardless of whether kidney function monitoring tests are required as a routine safety monitoring procedure in the study, if the investigator or sponsor deems it necessary to further assess kidney safety and quantify kidney function, then these test results should be managed and followed per standard of care.

10.7.2. Age-Specific Kidney Function Calculation Recommendations

10.7.2.1. Adults (18 Years and Above)—2021 CKD-EPI Equations¹⁴

2021 CKD-EPI Scr-Scys Combined	Scr (mg/dL)	Scys (mg/L)	Recommended eGFR Equation
Female	if ≤0.7	if ≤0.8	$eGFR = 130 \times (Scr/0.7)^{-0.219} \times (Scys/0.8)^{-0.323} \times (0.9961)^{Age}$
Female	if ≤0.7	if>0.8	eGFR = $130 \times (\text{Scr}/0.7)^{-0.219} \times (\text{Scys}/0.8)^{-0.778} \times (0.9961)^{\text{Age}}$
Female	if >0.7	if ≤0.8	eGFR = $130 \times (\text{Scr}/0.7)^{-0.544} \times (\text{Scys}/0.8)^{-0.323} \times (0.9961)^{\text{Age}}$
Female	if >0.7	if>0.8	eGFR = $130 \times (\text{Scr}/0.7)^{-0.544} \times (\text{Scys}/0.8)^{-0.778} \times (0.9961)^{\text{Age}}$
Male	if ≤0.9	if ≤0.8	eGFR = $135 \times (\text{Scr}/0.9)^{-0.144} \times (\text{Scys}/0.8)^{-0.323} \times (0.9961)^{\text{Age}}$
Male	if ≤0.9	if >0.8	eGFR = $135 \times (\text{Scr}/0.9)^{-0.144} \times (\text{Scys}/0.8)^{-0.778} \times (0.9961)^{\text{Age}}$
Male	if >0.9	if ≤0.8	eGFR = $135 \times (\text{Scr}/0.9)^{-0.544} \times (\text{Scys}/0.8)^{-0.323} \times (0.9961)^{\text{Age}}$
Male	if>0.9	if>0.8	eGFR = $135 \times (\text{Scr}/0.9)^{-0.544} \times (\text{Scys}/0.8)^{-0.778} \times (0.9961)^{\text{Age}}$

10.7.3. Adverse Event Grading for Kidney Safety Laboratory Abnormalities

AE grading for decline in kidney function (ie, eGFR or eCrCl) will be according to KDIGO criteria.

10.8. Appendix 8: ECG Findings of Potential Clinical Concern

ECG Findings That May Qualify as AEs

- Marked sinus bradycardia (rate <40 bpm) lasting minutes.
- New PR interval prolongation >280 ms.
- New prolongation of QTcF to >480 ms (absolute) or by ≥60 ms from baseline.
- New-onset atrial flutter or fibrillation, with controlled ventricular response rate: ie, rate <120 bpm.
- New-onset type I second-degree (Wenckebach) AV block of >30 seconds' duration.
- Frequent PVCs, triplets, or short intervals (<30 seconds) of consecutive ventricular complexes.

ECG Findings That May Qualify as SAEs

- QTcF prolongation >500 ms.
- New ST-T changes suggestive of myocardial ischemia.
- New-onset LBBB (QRS complex>120 ms).
- New-onset right bundle branch block (QRS complex>120 ms).
- Symptomatic bradycardia.
- Asystole:
 - In awake, symptom-free participants in sinus rhythm, with documented periods
 of asystole ≥3.0 seconds or any escape rate <40 bpm, or with an escape rhythm
 that is below the AV node.
 - In awake, symptom-free participants with atrial fibrillation and bradycardia with 1 or more pauses of at least 5 seconds or longer.
 - Atrial flutter or fibrillation, with rapid ventricular response rate: rapid = rate >120 bpm.
- Sustained supraventricular tachycardia (rate >120 bpm) ("sustained" = short duration with relevant symptoms or lasting >1 minute).

- Ventricular rhythms >30 seconds' duration, including idioventricular rhythm (HR <40 bpm), accelerated idioventricular rhythm (HR >40 bpm to <100 bpm), and monomorphic/polymorphic ventricular tachycardia (HR >100 bpm [such as torsades de pointes]).
- Type II second-degree (Mobitz II) AV block.
- Complete (third-degree) heart block.

ECG Findings That Qualify as SAEs

- Change in pattern suggestive of new myocardial infarction.
- Sustained ventricular tachyarrhythmias (>30 seconds' duration).
- Second- or third-degree AV block requiring pacemaker placement.
- Asystolic pauses requiring pacemaker placement.
- Atrial flutter or fibrillation with rapid ventricular response requiring cardioversion.
- Ventricular fibrillation/flutter.
- At the discretion of the investigator, any arrhythmia classified as an adverse experience.

The enumerated list of major events of potential clinical concern are recommended as "alerts" or notifications from the core ECG laboratory to the investigator and Pfizer study team, and not to be considered as all-inclusive of what to be reported as AEs/SAEs.

10.9. Appendix 9: Prohibited Concomitant Medications That May Result in DDI

[figure not shown]
The prohibited concomitant medications listed below should not be taken with PF-07081532 for the period of time at least equal to the required washout period listed in the table, and throughout the conduct of the study.

[figure not shown]
The Pfizer study team is to be notified of any prohibited medications taken during the study. After consulting with the sponsor, the investigator will make a judgment on the ongoing participation of any participant with prohibited medication use during the study.

[figure not shown]
This list of drugs prohibited for potential DDI concerns with the IMP may be revised during the course of the study with written notification from sponsor, to include or exclude specific drugs or drug categories for various reasons (eg, emerging DDI results for the IMP, availability of new information in literature on the DDI potential of other drugs).

This is not an all-inclusive list. Site staff should consult with the sponsor or designee with any questions regarding potential DDI.

Investigators should consult the product label for any other medication used during the study for information regarding medication that is prohibited for concomitant use.

10.10. Appendix 10: Other Prohibited Prior/Concomitant Medications

The following medications are prohibited until the follow-up visit, unless stated otherwise. If a participant receives a prohibited medication, the investigator should contact the sponsor clinician or sponsor medical monitor to determine if the participant should be included in the study/continued in the study.

Drug Classes and/or Drugs	Timeframe of Restriction
Other GLP-1R agonists	90 days prior to Screening visit (S1) until final follow-up contact
DPP-4 inhibitors, pramlintide, repaglinide	Screening visit (S1) until final follow-up contact
Systemic glucocorticoids such as prednisone, dexamethasone, triamcinolone, budesonide, betamethasone. Note: As an exception, steroid-containing inhalers, nasal sprays and topical formulations are permitted.	Screening visit (S1) until final follow-up contact
Immunosuppressants such as cyclosporine and tacrolimus	Screening visit (S1) until final follow-up contact
Cannabinoids (eg, medically prescribed THC)	Screening visit (S1) until final follow-up contact

10.11. Appendix 11: Abbreviations

The following is a list of abbreviations that may be used in the protocol.

Abbreviation	Term
Abs	absolute
ADL	activity/activities of daily living
AE	adverse event
AKI	acute kidney injury
ALT	alanine aminotransferase
ANOVA	Analysis of variance
AST	aspartate aminotransferase
AUC	area under the curve
AV	atrioventricular
AxMP	auxiliary medicinal product
BBS	Biospecimen Banking System
β-hCG	β-human chorionic gonadotropin
BMI	body mass index
BP	blood pressure
bpm	beats per minute
BSA	body surface area
BUN	blood urea nitrogen
cAMP	cyclic adenosine monophosphate
CFR	Code of Federal Regulations
CI	confidence interval
CIOMS	Council for International Organizations of Medical Sciences
CK	creatine kinase
CKD	chronic kidney disease
CKD-EPI	chronic kidney disease epidemiology
CL	clearance
CL/F	apparent clearance
CL _u /F	unbound CL/F
C_{max}	maximum plasma concentration
C _{max,u}	unbound C _{max}
CO_2	carbon dioxide (bicarbonate)
COVID-19	coronavirus disease 2019
CCI	
CRF	case report form
CRO	contract research organization
CRU	clinical research unit
CSR	Clinical Study Report
CT	clinical trial
CTIS	Clinical Trial Information System

Abbreviation	Term
CCI	
DBP	diastolic blood pressure
DCT	data collection tool
DDI	drug-drug interaction
DHT	digital health technology
DICI	drug-induced creatinine increase
DIKI	drug-induced kidney injury
DILI	drug-induced liver injury
DNA	deoxyribonucleic acid
EC	ethics committee
ECC	emergency contact card
ECG	electrocardiogram or electrocardiography
eCrCl	estimated creatinine clearance
eCRF	electronic case report form
EDB	exposure during breastfeeding
E-DMC	External Data Monitoring Committee
EDP	exposure during pregnancy
EFD	embryo fetal development
eGFR	estimated glomerular filtration rate
EOT	end of treatment
eSAE	electronic serious adverse event
EU	European Union
EudraCT	European Union Drug Regulating Authorities Clincal Trials
	(European Clinical Trials Database)
FDA	Food and Drug Administration
FIH	first-in-human
FPG	fasting plasma glucose
FSBG	fingerstick blood glucose
FSH	follicle-stimulating hormone
fu	fraction unbound in plasma/unbound fraction
GCP	Good Clinical Practice
GGT	gamma-glutamyl transferase
GI	gastrointestinal
GLP-1	glucagon-like peptide-1
GLP-1R	glucagon-like peptide-1 receptor
Н	hour
HbA1c	hemoglobin A1c
HAE	hypoglycemic adverse event(s)
HR	heart rate
HRT	hormone replacement therapy
IB	Investigator's Brochure

Abbreviation	Term
ICD	informed consent document
ICH	International Council for Harmonisation of Technical
	Requirements for Pharmaceuticals for Human Use
ID	identification
IMP	investigational medicinal product
IND	Investigational New Drug
INR	international normalized ratio
IP	investigational product
IPAL	Investigational Product Accountability Log
IPM	investigational product manual
IRB	Institutional Review Board
IV	Intravenous(ly)
IVGTT	intravenous glucose tolerance test
K ₂ EDTA	ethylene diamine tetraacetic acid
KDIGO	Kidney Disease Improving Global Outcomes
LBBB	left bundle branch block
LFT	liver function test
MCH	mean corpuscular hemoglobin
MCHC	mean corpuscular hemoglobin concentration
MCV	mean corpuscular volume
MDRD	modification of diet in renal disease
MEN2	multiple endocrine neoplasia type 2
MOA	mechanism of action
MQI	medically qualified individual
MTC	medullary thyroid cancer
N/A	not applicable
NIMP	noninvestigational medicinal product
NOAEL	no-observed-adverse-effect level
NRU	neutral red uptake
CCI	
PD	pharmacodynamic(s)
PE	physical examination
PI	principal investigator
PK	pharmacokinetic(s)
PO	oral
CCI	
PR	pulse rate
PSSA	Pfizer's Serious Adverse Event Submission Assistant
PT	prothrombin time
PVC	premature ventricular contraction/complex
QD	once daily

Abbreviation	Term
QTc	corrected QT interval
QTcF	QTc corrected using Fridericia's formula
qual	qualitative
RBC	red blood cell
RNA	ribonucleic acid
S1	Screening visit 1
S2	Screening visit 2
SAE	serious adverse event
SAP	Statistical Analysis Plan
SARS-CoV-2	severe acute respiratory syndrome coronavirus 2
SBP	systolic blood pressure
Scr	serum creatinine
Scys	serum cystatin C
SoA	schedule of activities
SOC	system organ class
SOP	standard operating procedure
SRSD	Single Reference Safety Document
SSID	study-specific identification
SUSAR	Suspected Unexpected Serious Adverse Reaction
T2DM	type 2 Diabetes Mellitus
t _{1/2}	terminal half-life
T bili	total bilirubin
THC	tetrahydrocannabinol
T _{max}	time for C _{max}
UACR	urine albumin/creatinine ratio
CCI	
ULN	upper limit of normal
US	United States
V _Z /F	apparent volume of distribution
V _{z,u} /F	unbound V _z /F
WBC	white blood cell
WOCBP	woman/women of childbearing potential

1. VERSION HISTORY

Table 1. Summary of Changes

Version/ Date	Associated Protocol Amendment	Rationale	Specific Changes
1	Original	N/A	N/A
6 Sep 2022	03 Jun 2022		

2. INTRODUCTION

The purpose of this study is to characterize the effect of varying degrees of renal impairment on the PK, safety and tolerability of PF-07081532. PF-07081532 is an oral GLP-1R agonist that is currently being investigated as a chronic therapy to improve glycemic control in adult participants with T2DM. CKD occurs in 20-40% of patients with diabetes and may be present at the time of diagnosis of T2DM.

[figure not shown]
This statistical analysis plan (SAP) provides the detailed methodology for summary and statistical analyses of the data collected in Study C3991007.

2.1. Modifications to the Analysis Plan Described in the Protocol

Not Applicable

2.2. Study Objectives, Endpoints, and Estimands

Objectives	Endpoints	
Primary:	Primary:	
To compare the PK of PF-07081532 following administration of a single oral dose in adult participants with T2DM and varying degrees of renal impairment relative to age- and body weight-matched participants with T2DM, without renal impairment.	 Plasma: Cmax, AUCinf, AUClast*, fu, Cmax,u, AUCinf,u and AUClast,u*, as data permit. 	
Secondary:	Secondary:	
To evaluate the safety and tolerability of a single oral dose of PF-07081532 when administered to adult participants with T2DM and varying degrees of renal impairment relative to age- and body weight-matched participants with T2DM, without renal impairment.	 Assessment of treatment emergent AEs, clinical laboratory abnormalities, vital signs, ECG parameters. 	
Tertiary/Exploratory:	Tertiary/Exploratory:	
To compare additional plasma PK parameters of PF-07081532 following administration of a single oral dose in adult participants with T2DM and varying degrees of renal impairment relative to age- and body weight-matched participants with T2DM, without renal impairment.	 Plasma: CL/F, CL_w/F, V_z/F, V_{z,w}/F, T_{max} and t_{1/2} as data permit. 	

^{*} AUC_{last} and AUC_{last,u} will be treated as primary endpoints if data do not permit robust estimation of AUC_{inf} and AUC_{inf,u}, otherwise they will be treated as tertiary endpoints.

2.2.1. Primary Estimand(s)

Not applicable because C3991007 is a Phase 1 study with no estimands on PK endpoints

2.2.2. Secondary Estimand(s)

Not applicable because C3991007 is a Phase 1 study with no estimands on safety endpoints

2.2.3. Additional Estimand(s)

Not applicable because C3991007 is a Phase 1 study with no estimands on other endpoints

2.3. Study Design

This is an open-label, single-dose, parallel-group study to investigate the effect of varying degrees of renal function on the PK of PF-07081532 after a single, oral 20 mg dose administered in the fed state (standard, non-high fat breakfast). Safety and tolerability will be evaluated throughout the study. A total of approximately 32 participants with T2DM and varying degrees of renal function will be dosed in the study as shown in Table 2. If recruitment of participants with eGFR <30 mL/min proves prohibitive, the number of participants to be enrolled in the group with severe impairment may be flexible (6-8 participants).

Table 2. Renal Function Categories Based on eGFR
--

Group	Renal Impairment	eGFR ^a (mL/min) ^a	Number of Participants
1	None (Normal Renal Function)	≥90	8
2	Mild	60-89	8
3	Moderate	30-59	8
4	Severe	<30	8^b

a. Note:participants on dialysis will be placed in Group 4 regardless of unnormalized eGFR value.

Categorization of participants into Groups 2-4 will be done based on eGFR values determined at the screening visit, as described in Section 4.1 of the protocol.

b. 2-4 participants on dialysis are permitted (not required). If requirement proves to be prohibitive, study may dose 6-8 participants with severe renal impairment.

Staged Enrollment of Study Groups

- Participants will be dosed in a staged manner such that those with moderate and severe renal impairment (Groups 3 and 4) will be enrolled first.
- Recruitment of participants with mild renal impairment (Group 2) will initiate when approximately 50% of the participants in Groups 3 and 4 have been dosed.

Approval from the sponsor is required before proceeding with recruitment of Group 2.

- An average value for age and weight for Groups 2, 3, and 4 will be determined and participants in Group 1 will be recruited to match the average demographics (at a minimum, age and weight, and as much as practically possible gender) across the pooled Groups 2-4.
- Therefore, recruitment of participants without renal impairment (Group 1) may start when approximately 75% of total participants across Groups 2-4 (ie, approximately 17-18 participants) have been dosed.

Approval from the sponsor is required before proceeding with recruitment of Group 1.

3. ENDPOINTS AND BASELINE VARIABLES: DEFINITIONS AND CONVENTIONS

Baseline is defined as the last pre-dose assessment for all endpoints, unless otherwise specified.

3.1. Primary Endpoint(s)

 PF-07081532 Plasma Pharmacokinetic parameters: C_{max}, AUC_{inf}, AUC_{last}, fu, C_{max,u}, AUC_{inf,u}, AUC_{last,u} as data permit.

The plasma PK parameters in Table 3 will be derived from concentration-time profiles using standard non-compartmental analysis methods (with the exception of fu that will be directly determined by the analytical lab):

Table 3. Summary of Plasma PK Parameters of PF-07081532 to be calculated

Parameter	Analysis Scale	PF-07081532 20mg
C _{max}	ln	A, D
AUCinf*	ln	A, D
AUC _{last} ⁺	ln	A, D
fu	ln	A, D
C _{max,u}	ln	A, D

AUCinf,u*	ln	A, D
AUC _{last,u} +	ln	A, D

^{*=}if data permits. + AUC_{last} and AUC_{last,u} will be treated as primary endpoints if data do not permit robust estimation of AUC_{inf} and AUC_{inf,u}. Abbreviations: A = analyzed using a statistical model; D=displayed with descriptive statistics as outlined in Table 8. in Section 6.1.1.1; ln=natural-log transformed; R=raw (untransformed).

The plasma PK parameters for unbound PF-07081532 will be calculated as described in Table 4:

Table 4. Summary of Plasma PK parameters of Unbound PF-07081532 to be calculated

Parameter	Method of Determination
AUC _{last,u} +	$fu \times AUC_{last}$
AUCinf,u*	fu × AUC _{inf} *
C _{max,u}	$fu \times C_{max}$

^{*=}if data permits. + AUC_{last} and AUC_{last,u} will be treated as primary endpoints if data do not permit robust estimation of AUC_{inf} and AUC_{inf,u},

3.2. Secondary Endpoint(s)

Assessment of treatment emergent AEs, clinical laboratory abnormalities, vital signs, ECG parameters.

An adverse event is considered treatment emergent (TEAE) relative to a given treatment if:

• the event starts during the effective duration of treatment (i.e. starting on or after the dose of PF-07081532 but before this dose plus lag time)

The effective duration of treatment is determined by the lag time. Any event occurring within the lag time is attributed to the corresponding treatment. The lag time is defined by the Pfizer Standard of 365 days post last dose of IP.

A 3-tier approach for summarizing AEs will not be used due to the low number of participants planned to be recruited.

The following data are considered in standard safety summaries (see protocol for collection days and list of parameters):

- adverse events,
- laboratory data,
- · vital signs data,
- ECG results.

For laboratory, vital signs and ECG data, baseline will be defined as the last pre-dose measurement, unless otherwise specified.

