8.4.1. Time Period and Frequency for Collecting AE and SAE Information

The time period for actively eliciting and collecting AEs and SAEs ("active collection period") for each participant begins from the time the participant provides informed consent, which is obtained before undergoing any study-related procedure and/or receiving study intervention), through and including a minimum of 28 calendar days, except as indicated below, after the last administration of the study intervention.

Follow-up by the investigator continues throughout the active collection period and until the AE or SAE or its sequelae resolve or stabilize at a level acceptable to the investigator.

When a clinically important AE remains ongoing at the end of the active collection period, follow-up by the investigator continues until the AE or SAE or its sequelae resolve or stabilize at a level acceptable to the investigator and Pfizer concurs with that assessment.

For participants who are screen failures, the active collection period ends when screen failure status is determined.

If the participant withdraws from the study and also withdraws consent for the collection of future information, the active collection period ends when consent is withdrawn.

If a participant permanently discontinues or temporarily discontinues study because of an AE or SAE, the AE or SAE must be recorded on the CRF and the SAE reported using the CT SAE Report Form.

Investigators are not obligated to actively seek information on AEs or SAEs after the participant has concluded study participation. However, if the investigator learns of any SAE, including a death, at any time after a participant has completed the study, and they consider the event to be reasonably related to the study intervention, the investigator must promptly report the SAE to Pfizer using the CT SAE Report Form.

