- For each AE or SAE, the investigator must document in the medical notes that they have reviewed the AE or SAE and have provided an assessment of causality.
- There may be situations in which an SAE has occurred and the investigator has minimal information to include in the initial report to the sponsor. However, it is very important that the investigator always make an assessment of causality for every event before the initial transmission of the SAE data to the sponsor.
- The investigator may change their opinion of causality in light of follow-up information and send an SAE follow-up report with the updated causality assessment.
- The causality assessment is one of the criteria used when determining regulatory reporting requirements.
- If the investigator does not know whether or not the study intervention caused the event, then the event will be handled as "related to study intervention" for reporting purposes, as defined by the sponsor. In addition, if the investigator determines that an SAE is associated with study procedures, the investigator must record this causal relationship in the source documents and CRF, and report such an assessment in the dedicated section of the CT SAE Report Form and in accordance with the SAE reporting requirements.

Follow-Up of AEs and SAEs

- The investigator is obligated to perform or arrange for the conduct of supplemental
 measurements and/or evaluations, as medically indicated or as requested by the
 sponsor, to elucidate the nature and/or causality of the AE or SAE as fully as
 possible. This may include additional laboratory tests or investigations,
 histopathological examinations, or consultation with other healthcare providers.
- If a participant dies during participation in the study or during a recognized follow-up period, the investigator will provide Pfizer Safety with a copy of any postmortem findings, including histopathology.
- New or updated information will be recorded in the originally submitted documents.
- The investigator will submit any updated SAE data to the sponsor within 24 hours of receipt of the information.

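### SAP 3.2 defines treatment-emergent AEs by start date alone, so an AE that begins between consent and dosing and worsens on or after the dose can drop out of the TEAE summary

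*SAP*

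**What the plan says.** **Endpoint.** The secondary endpoint in SAP 3.2 is "Assessment of treatment emergent AEs, clinical laboratory abnormalities, vital signs, ECG parameters". The protocol lists the same endpoint in Section 3 but does not define treatment-emergent.

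**Rule.** SAP 3.2 gives a single condition: "the event starts during the effective duration of treatment (i.e. starting on or after the dose of PF-07081532", with the window closing at the dose plus a lag time. It then fixes the lag: "The lag time is defined by the Pfizer Standard of 365 days post last dose of IP".

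**Collection.** Under protocol 8.4.1 the active collection period "begins from the time the participant provides informed consent" and runs "through and including a minimum of 28 calendar days" after the dose. The Schedule of Activities places consent at visit S1, which may be up to 28 days before Day 1, and the follow-up contact 28 to 35 days after dosing.

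**Recording.** Protocol 10.3.1 treats a flare of a long-standing or recurring condition, in frequency or intensity, as an AE. Protocol 10.3.3 asks for an intensity rating for each AE. In its follow-up part it adds: "New or updated information will be recorded in the originally submitted documents".

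**Reporting.** SAP 6.2.1 summarises AEs by group and overall under sponsor standards. SAP 6 says that data from before baseline are listed only, unless stated otherwise.

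**The concern.** A definition of treatment emergence usually has two limbs: the event is new after dosing, or it was present before dosing and got worse. SAP 3.2 has only the first. Because AEs are collected from consent, the database will be able to hold events with a pre-dose start. Take a participant with mild nausea recorded after S1 that becomes severe after the dose. If the site keeps one record with its original start date, the stated rule does not flag the event, whatever its later course.

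TEAEs are the first-listed component of the secondary endpoint, and the objective is a comparison with participants without renal impairment. There is no placebo arm, so the tabulation by group is the main safety contrast. Protocol 2.2.4.1 names nausea and vomiting as the most frequent TEAEs after single doses, and these are symptoms that can already be present before dosing.

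**Working it through.** The plan states no figure on this point, so there is none to reproduce. The check sets the sections side by side and adds two small calculations.

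**1. Can an AE with a pre-dose start be in the database?** Yes. Collection starts at consent (protocol 8.4.1), and S1 can be up to 28 days before Day 1.

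- With follow-up at 28 days, the share of the collection period before dosing is at most 28 / (28 + 28) = 50%.
- With follow-up at 35 days, it is at most 28 / (28 + 35) = 44%.

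These are shares of time, not of events.

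**2. Can such an AE meet the rule in SAP 3.2?** Not while it keeps its start date. The 365-day lag only extends the far end of the window. It is longer than the 28 to 35 days of post-dose follow-up and does nothing at the near end.

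**3. Does another section add a worsening limb?** No. SAP 6.2.1 adds none, and SAP 6 leaves pre-baseline data to listings.

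**4. Does AE recording close the gap?** In part.

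| Situation | Outcome under the documents |
|---|---|
| Chronic or intermittent condition predating the study, worse after the dose | An AE in its own right under protocol 10.3.1. If recorded with a post-dose start it meets the SAP rule. |
| AE starting between consent and dosing, worsening entered as a new record | Post-dose start, so it meets the SAP rule. Neither document requires the new record. |
| AE starting between consent and dosing, kept as one record, worse or serious after the dose | Pre-dose start, so it is not a TEAE. |

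Only the third row is exposed.

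**5. How much does one participant count?** Protocol Table 1 plans 8 per group and allows 6 to 8 in the severe group.

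- 1 / 8 = 12.5 percentage points.
- 1 / 6 = 16.7 percentage points.

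This is the change in a group's incidence when one participant is missed. It applies to overall TEAE incidence only if that participant has no other TEAE. For a single preferred term it applies only if the participant has no other TEAE coded to that term.

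**The case against.** The case against giving this much weight is good, and most of it stands.

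- **Start dates.** A reader might infer from the follow-up text in protocol 10.3.3 that a worsening must go into the old record and keep the pre-dose start date. The documents do not say so. The sentence stands between postmortem findings and the 24-hour rule for updated SAE data. It reads as follow-up of reports already submitted, and it is silent on start dates. One-record handling is therefore possible but not mandated.
- **Scope.** Chronic comorbidity is largely protected by protocol 10.3.1. Laboratory, vital-sign and ECG data use the last pre-dose value as baseline, so worsening there is unaffected. SAEs are reported within 24 hours whatever their TEAE status. It would be wrong to say that the event is lost from the secondary safety endpoint as a whole. It is lost from the TEAE summary and remains in the listings.
- **Bias across groups.** A reader might expect sicker groups to carry more open events into dosing, so that the rule makes the renal groups look more alike. No section gives the number of AEs open at dosing in any group. Protocol 5.4 allows Groups 2 to 4 to be rescreened after mild intercurrent illness, but only once it has resolved, which works against carry-over.
- **Unseen documents.** The CRF Completion Requirements document (protocol 10.1.7) or the sponsor reporting standards may already tell sites or programmers what to do. That cannot be checked here.

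What the objection does not remove is the explicit definition. Taken as written, SAP 3.2 excludes the event in the third row of the table, and whether that row occurs depends on how each site keeps its records.

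**Conclusion.** The point holds in a narrow form. SAP 3.2 omits from the TEAE summary an AE that starts between consent and dosing, stays as one record, and increases in severity or becomes serious on or after the dose. This rests on two assumptions: that at least some sites keep a single record, and that no unseen sponsor standard overrides the SAP's stated rule.

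The number of participants affected cannot be derived from the documents. In a single-dose study of about 32 participants it is probably small. The 12.5 and 16.7 point figures show how much one participant weighs. They are not estimates of bias, and no direction across the renal groups is supported. The safety summaries are descriptive and no hypothesis test depends on them. The change is still worth making, because it is cheap and it takes the count out of the hands of site recording habits.

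**What to change.** Add a second limb to the treatment-emergent definition in SAP 3.2: *or the event starts before the dose and increases in severity, or becomes serious, on or after the dose.*

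The limb can be programmed only if the date of worsening is known. Protocol 10.3.3 asks for an intensity rating for each AE but does not ask when that intensity changed. The CRF guidance should therefore capture the date by one of two routes:

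- a dated change of severity or seriousness within the existing record; or
- a new record starting on the date of worsening, worded so that it is consistent with protocol 10.3.3.

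These are alternatives. With new records the existing start-date rule already captures the event, and the added clause serves as a safeguard. Choose one route, so that the same worsening is not counted as two events, and first check whether the CRF Completion Requirements document already covers it.

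The cost is one SAP clause, some programming and a CRF guidance note. The TEAE count may be slightly higher. Visits and sample size do not change.
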